### 7.1 Time Period and Frequency for Collecting AE Information

All clinical events will be collected from the signing of the informed consent form (ICF) until the final visit at the time points specified in the SoA (Section 1.1).

Events that begin before randomization but after obtaining informed consent will be recorded on the Medical History/Current Medical Conditions section of the eCRF.

### 7.2 Regulatory Reporting Requirements for SAEs

Clinical events, as outlined in Section 7, will be collected and reported in aggregate and unblinded to study group to the Data Safety Monitoring Board (DSMB). Other serious adverse events will not be collected. The study DSMB will be responsible for the ongoing evaluation of participants' safety (eg, event trends). Site investigators may report individual SAEs to their IRBs according to their local IRB requirements.

### 7.3 Medical Device Incidents (Including Malfunctions, ADEs, UADEs)

Inclusion criteria for this study require that participants have an On-X aortic valve replacement and are at least 3 months following implantation. In order to fulfill regulatory reporting obligations worldwide, investigators are responsible for the detection and documentation of events meeting the definitions of device incident or malfunction that occur during the study.

The definition of a Medical Device Incident can be found in Section 10.1.

All valve-related Adverse Device Effects (ADEs) and Unanticipated Adverse Device Effects (UADEs) occurring from informed consent through the final study visit will be collected. ADEs and UADEs will be reported in aggregate unblinded to study group to the DSMB.

Investigators are responsible for reporting UADEs to their IRB within 10 working days of first learning of the event as per local requirements.

It is understood that complete information about an event may not be known at the time the initial report is recorded. The investigator must assess the causal relationship of the event to the study drug and the investigational device (including rationale for assessment) and should make every attempt to obtain as much information as possible concerning the event. Additional

information pertaining to an event should be reported as it becomes available. All UADEs will be followed to resolution or stabilization. Stabilization means the investigator does not expect any further improvement or worsening of the AE.

#### **7.4 Treatment of Overdose**

For this study, the following will be considered an overdose:

- any dose of apixaban greater than 15 mg within a 24-hour time period
- any dose of warfarin resulting in an INR above 7

No specific treatment is recommended for an overdose of apixaban or warfarin. If major bleeding occurs in the setting of an overdose of apixaban, prothrombin complex concentrate (PCC) or andexanet alfa may be used to reverse the anticoagulant effect of apixaban. If major bleeding occurs in the setting of an overdose of warfarin, fresh frozen plasma, PCC, or vitamin K may be used to reverse the anticoagulant effect of warfarin.

In the event of an overdose of apixaban or warfarin, the investigator should closely monitor the participant for bleeding.

Decisions regarding dose interruptions or modifications will be made by the investigator in consultation with the sponsor's Coordinating Investigator based on the clinical evaluation of the participant.

## 8 Statistical Considerations

### 8.1 Statistical Hypotheses

The primary efficacy outcome is the composite of valve thrombosis and valve-related thromboembolism. Assuming that time-to-event for the primary efficacy outcome is approximately exponentially distributed (ie, a constant hazard), the first co-primary analysis is to determine whether the hazard rate of the device using apixaban (test) is non-inferior to the hazard rate of the device using warfarin (control) by the margin of 1.75%/ pt-yr. The hypothesis statement is as follows:

$$H_0: \lambda_{\text{apixaban}} - \lambda_{\text{warfarin}} \geq 1.75\%/\text{pt-yr}$$

$$H_A: \lambda_{\text{apixaban}} - \lambda_{\text{warfarin}} < 1.75\%/\text{pt-yr},$$

where  $\lambda$  is the hazard rate of the primary efficacy outcome. The second co-primary analysis is to compare the hazard rate for the apixaban arm to two times the OPC for thromboembolism and valve thrombosis or 3.4%/pt-yr ( $= 2 \times 1.7\%/\text{pt-yr}$ ). (Error! Not a valid bookmark self-reference. et al., 2014)

Once non-inferiority has been met, we will test the hypothesis that the hazard rate of the device using apixaban (test) is superior to the hazard rate of the device using warfarin (control) for the primary efficacy outcome.

For major bleeding (primary safety outcome), the hypothesis test is to determine whether the hazard rate of the device using apixaban (test) is superior to the hazard rate of the device using warfarin (control). The hypothesis statement is as follows:

$$H_0: \lambda_{\text{apixaban}} - \lambda_{\text{warfarin}} \geq 0$$

$$H_A: \lambda_{\text{apixaban}} - \lambda_{\text{warfarin}} < 0,$$

where  $\lambda$  is the hazard rate of the primary safety outcome.

### 8.2 Sample Size Determination

Approximately 1000 participants will be randomly assigned to study intervention for an estimated total of 500 participants per intervention group with one-sided alpha of 2.5% and an approximate power of 90%. Since the OPC test does not require a statistical significance level, this study is powered for the NI test.

The assumed primary outcome rate is 1.75%/pt-yr with warfarin based on a review of literature available with the On-X aortic devices (Puskas et al., 2018; Tossios et al., 2007; On-X Original PMA #P000037, 2001; McNicholas et al., 2006; Chambers et al., 2013; and Wu et al., 2006). It was assumed that all historical trials enrolled a mixture of high and low risk population (HRP and LRP), but only the PROACT clinical trial (Puskas et al., 2014; Puskas et al., 2018) reported the proportion of high and low risk populations (65% and 35% respectively), which was taken into account to estimate the primary outcome rate for the trial.

The thromboembolism (TE), thrombosis and valve-related mortality (VRM) rates are coincident to the remaining events in the composite. Thus, the sample size will be based on a composite of TE, thrombosis and VRM rates. Except for the PROACT clinical trial data, the publications report the non-hierarchical event rate for VRM and TE. If a participant died due to a TE, it would be counted in both the VRM and the TE rate. The trial by Tossios et al., 2007 report the number of deaths related to TE (n=5) and all valve-related deaths (n=19). The percent of deaths due TE is 26%. It was assumed that for any publication that did not report the number of deaths related to TE that 26% of the deaths were due to TE. Thus, the VRM rates are reduced by 26%.

**Table 3** (see section 11) summarizes the available literature, the event rates and their variances. Since the number of historical trials to estimate the event rate in warfarin arm is not large, the Hartung-Knapp-Sidik-Jonkman (HKSJ) method was used to produce more robust estimates of variance of the event rate (IntHout et al., 2014). The pooled event rate of warfarin was estimated as 1.75%/pt-yr with a 95% confidence interval of 1.09%/pt-yr and 2.81%/pt-yr by a random effects HKSJ meta-analysis model with the R metafor package. We project that there will be a similar event rate with apixaban and set the non-inferiority margin for this study at 1.75%/pt-yr, equivalent to a doubling of the estimated event rate in warfarin arm.

To confirm that the non-inferiority margin preserves the treatment effect, we would need to estimate the treatment effect for the use of warfarin post-implantation as compared to placebo. There are no placebo-controlled trials of warfarin for patients with AVR. In the PROACT trial that randomized low risk AVR patients to warfarin (INR 2.0-3.0) or dual antiplatelet therapy (DAPT), the warfarin arm had a hazard rate of 1.15%/pt-yr and the DAPT arm had a hazard rate of 7.02%/pt-yr (detailed in Section 11, **Table 4**). Given the substantially higher event rate in the DAPT versus warfarin arm, we have conservatively assumed that DAPT was a placebo equivalent. Though not ideal, the treatment effect calculated from this data will be conservative (i.e., smaller) than the treatment effect estimated from a true placebo arm. However, the trial involving DAPT enrolled only low risk AVR patients (i.e., no chronic atrial fibrillation, left ventricular ejection fraction > 30 %, left atrium < 50mm diameter, no spontaneous echo contrasts in the left atrium, no neurological events, no hypercoagulability, and no left or right ventricular aneurysm).

To extrapolate these results to an all-comer AVR population, we employed a conversion factor. The event rate for warfarin in the low risk population is 1.15%/pt-yr, the meta-analysis above demonstrated a pooled event rate of 1.75%/pt-yr for warfarin-treated patients (INR 2.0-3.0), therefore the conversion factor was calculated to be 1.52 (= 1.75/1.15). The number of observed events (95% CI) with 26% reduction to VRM for TE overlap of DAPT in the low risk population is 20.2 (13.00, 30.89) using the Poisson distribution, which translated to an event rate (95% CI) of DAPT arm of 7.02% (4.51%/pt-yr, 10.72%/pt-yr). Multiplying by the conversion factor of 1.52, the DAPT event rate (95% CI) in an all-comer AVR population is 10.65%/pt-yr (6.85%/pt-yr, 16.28%/pt-yr).

Table 2 presents the estimated event rates and confidence intervals for warfarin, DAPT and apixaban in all-comer AVR population. Even if an event rate in apixaban arm is 5%/pt-yr, which is unlikely, the estimated upper 95% CI of the apixaban arm will still remain below the lower 95% CI of the event rate of DAPT.

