### 6.1 Efficacy Assessments

Efficacy will be assessed by the evaluation of the hazard rates of the primary efficacy outcome, the composite of valve thrombosis and valve-related thromboembolism. An independent Clinical Events Classification (CEC) Committee will adjudicate whether any valve thrombosis and/or valve-related thromboembolism event has occurred.

**Valve thrombosis:** defined as any thrombus not caused by infection attached to or near an implanted On-X valve that occludes part of the blood flow path, interferes with valve function, or is sufficiently large to warrant treatment other than continued oral anticoagulation. Furthermore, valve thrombus found at autopsy in a participant whose cause of death was not valve related or found at operation for an unrelated indication will also be reported as valve thrombosis. ([Akins et al., 2008](#)).

**Valve-related thromboembolism:** defined as any thromboembolic stroke, thromboembolic transient ischemic attack (TIA), thromboembolic myocardial infarction, or arterial

thromboembolism to another organ or limb, occurring after the immediate perioperative period and not associated with infection or intracardiac tumor. The independent CEC committee will determine whether a thromboembolism was related to the On-X valve based on clinical evaluation, surgery, and autopsy data. If the thromboembolism is determined to be of unknown origin after clinical evaluation, surgery, and/or autopsy, the thromboembolism will be conservatively considered to be related to the On-X valve.

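### The 1.75%/pt-yr planning rate includes valve-related deaths that the primary outcome leaves out, so the margin is not established as a doubling for the outcome being tested

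*Combined protocol and SAP*

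**What the plan says.** Protocol 8.1 defines what is tested: "The primary efficacy outcome is the composite of valve thrombosis and valve-related thromboembolism". The objectives, protocol 6.1 and both SAP versions agree, and none adds death.

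Protocol 8.2 opens its rate assumption with "The assumed primary outcome rate is 1.75%/pt-yr with warfarin". It then says that TE, thrombosis and VRM "rates are coincident to the remaining events in the composite" and concludes: "Thus, the sample size will be based on a composite of TE, thrombosis and VRM rates". To avoid counting fatal TE twice, VRM is cut by a fraction taken from the German single-centre series (5 of 19 valve-related deaths): "The percent of deaths due TE is 26"%. The other 74% of VRM stays in. PROACT is treated as different: "Except for the PROACT clinical trial data, the publications report the non-hierarchical event rate for VRM and TE".

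The pooled result, 1.75%/pt-yr (95% CI 1.09 to 2.81), then sets the margin: the sponsor "set the non-inferiority margin for this study at 1.75%/pt-yr, equivalent to a doubling of the estimated event rate in warfarin arm". The effect-preservation argument (1.75/4.04, about 43%) uses the same death-inclusive counts, through Table 4. SAP version 1.4, section 6.1.8, carries 1.75% forward and refers to protocol 8.2 for the margin justification.

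**The concern.** The planning rate and the tested outcome have different components. The reason given for including VRM appeals to remaining events in the composite, but the tested composite has none beyond TE and thrombosis.

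An absolute margin means a doubling only if the control rate equals the margin. If the warfarin rate for TE plus thrombosis is lower than 1.75%, the same margin allows more than a doubling. A reader told that the margin equals a doubling could then take a non-inferior result as excluding one. The second co-primary test would not fill the gap: twice 1.2% is 2.4%, which is under the 3.4%/pt-yr limit. The 43% figure would likewise describe an outcome that is not tested.

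**Working it through.** **1. The plan's sample size reproduces.** Inputs from protocol 8.2: rate λ = 1.75%/pt-yr in both arms, margin Δ = 1.75%, one-sided alpha 2.5%, 90% power, 1-year accrual with half enrolled by 40% of it, 2-year minimum follow-up, loss hazard 0.026. I took entry as truncated exponential. The probability of an observed event is then P = 0.0425, and

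N = 2 × (1.960 + 1.282)² × (2λ²/P)/Δ² = 989, against the stated 990.

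Power at N = 1,000 is 90.3%, as in SAP Table 1. Exposure is 500 × 0.0425/0.0175 = about 1,214 pt-yr per arm.

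**2. Table 3 totals are TE + thrombosis + 0.74 × VRM.** The two PROACT control groups are merged, as in the table.

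| Source | TE | Thrombosis | VRM | Computed | Table 3 | pt-yr |
|---|---|---|---|---|---|---|
| UK/Spain/Greece, 2013 | 8 | 0 | 7 | 13.18 | 13.2 | 1,360 |
| USA, 2006 | 6 | 0 | 5 | 9.70 | 9.7 | 659 |
| Original PMA, 2001 | 7 | 0 | 1 | 7.74 | 7.7 | 411.8 |
| PROACT controls | 20 | 2 | 11 | 30.14 | 30.1 | 1,433.5 |
| Germany, 2007 | 16 | 0 | 19 | 30.06 | 30.1 | 1,069.4 |
| South Africa, 2006 | 2 | 0 | 7 | 7.18 | 7.2 | 172.5 |
| Total | 59 | 2 | 50 | 98.0 | | 5,106.2 |

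Deaths not due to TE: 0.74 × 50 = 37, and 37/98 = 38%. The exact 95% interval for 5/19 is 9% to 51%, which puts these deaths at 24 to 45 of 50, or 29% to 43% of planning events.

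**3. Rate for the tested components.** Crude: (59 + 2)/5,106.2 = 1.19%/pt-yr, against 98/5,106.2 = 1.92% with deaths. Random-effects pooling of log rates (REML, Hartung-Knapp interval):

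- six sources: 1.23% (0.80 to 1.87)
- without the South African study: 1.22% (0.72 to 2.08)
- PROACT groups split: 1.20% (0.73 to 1.97)
- both changes: 1.19% (0.66 to 2.17)

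**4. The plan's 1.75% does not reproduce from Table 3.** Its interval is symmetric about 1.75 on the log scale (√(1.09 × 2.81) = 1.75), yet the six-source log model gives 2.00% (1.20 to 3.34) on the death-inclusive counts. Other random-effects variants give 1.88 to 2.00%. The pooled figures in step 3 are therefore not like for like with 1.75%. The component counts in step 2 do not depend on this.

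**5. Ratio allowed by the margin: (rate + 1.75)/rate.**

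| Warfarin rate (%/pt-yr) | Basis | Allowed ratio |
|---|---|---|
| 0.66 | lowest lower limit in step 3 | 3.7 |
| 1.19 | crude | 2.5 |
| 1.23 | pooled, six sources | 2.4 |
| 1.41 | crude, all 11 PROACT deaths added (72/5,106.2) | 2.2 |
| 1.53 | PROACT controls alone (22/1,433.5) | 2.1 |
| 1.70 | the objective performance criterion (OPC) | 2.0 |
| 1.73 | PROACT controls plus 26% of their deaths (24.86/1,433.5) | 2.0 |
| 1.75 | plan | 2.0 |
| 2.17 | highest upper limit in step 3 | 1.8 |

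**6. Chance that a true doubling passes the SAP confidence-interval rule.** Exact Poisson enumeration at 1,214 pt-yr per arm: 19% from 1.20%, 17% from 1.23%, 6% from 1.53%, 3.4% from 1.70% and 2.8% from 1.75%. SAP Table 2 simulates type I error only for 1.75% against 3.50%, the base rate at which margin and doubling coincide.

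A boundary example at 1.24% on warfarin (15 events) against 24 on apixaban: upper bound (24 − 15)/1,214 + 1.96 × √39/1,214 = 1.7496%, which passes. The rate ratio is 1.6 with a 95% upper limit of 3.05.

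**7. Power.** At equal rates of 1.20 to 1.25%, power against the 1.75% margin is about 97%.

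**The case against.** The plan does not hide the deaths: protocol 8.2 says VRM is included and Tables 3 and 4 itemise it. SAP 6.1.8 acknowledges uncertainty in the warfarin rate, and a Cox sensitivity analysis with a hazard-ratio margin of 2 is prespecified with its power tabulated. Any absolute margin implies a ratio that moves with the control rate. No decision rule mentions a doubling; success is worded as apixaban being a reasonable alternative. All of this stands, and it limits the point to a label and what is inferred from it.

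There is also support in the documents for a two-component rate near 1.75%. The OPC for TE plus valve thrombosis is 1.7%, although it covers mechanical aortic valves generally and the plan does not use it to justify the warfarin rate. PROACT controls give 1.53%, and 1.73% if 26% of their deaths are assumed to be fatal TE counted only under VRM. The trial's definition may also capture more events than the historical reports: peripheral TE was counted only where reported, whereas for TE of unknown origin here "the thromboembolism will be conservatively considered to be related to the On-X valve". Some sources used INR targets other than 2.0 to 3.0.

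A reader might therefore go further and infer that the margin is demonstrably wider than a doubling. The documents do not support that: the intervals include 1.75% and the allowed ratio includes 2.0. Nor do they support reading the mismatch as a loss of power, because a lower event rate raises power against a fixed absolute margin.

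**Conclusion.** The concern holds in limited form. The 1.75%/pt-yr figure is a death-inclusive rate carrying the primary outcome's label. On the plan's own counts, TE plus thrombosis runs at about 1.2%/pt-yr, with intervals from roughly 0.7 to 2.2 depending on model and studies. The margin then allows about 2.4 to 2.5 times the warfarin rate at the best estimate, and roughly 1.8 to 3.7 across the variants. The doubling is not established for the tested outcome; it is not refuted either. The 43% figure has the same limitation.

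This rests on the Table 3 counts, the plan's 26% split (from 19 deaths) and, for the pass probabilities, 1,214 pt-yr per arm. Failure to reproduce 1.75% is a separate gap that affects how the two rates can be compared.

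Severity is minor to moderate: a stated figure and its interpretation need correcting, and no decision rule changes. SAP 6.1.3 says the study was stopped, so the wording of the study report now matters most.

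**What to change.** Keep the margin, the test and the sample size. Change the text as follows.

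1. In protocol 8.2 and SAP 6.1.8, state that 1.75% includes VRM, and give the TE plus thrombosis estimate beside it (about 1.2%/pt-yr), computed by the same method. Specify that method (scale, between-study variance estimator, studies included, handling of the two PROACT groups) so that 1.75% can be reproduced.
2. In protocol 8.2, replace the doubling statement with the allowed ratio at the two-component estimate (about 2.4 to 2.5), its sensitivity range (about 1.8 to 3.7), and 2.0 if the warfarin rate is 1.75%.
3. There and in the study report, state that meeting the absolute margin does not by itself exclude a doubling. The Cox sensitivity analysis with a hazard-ratio margin of 2.0 is the one that addresses it, with power of 40.6% at 1.25% and 52.9% at 1.75% (SAP Table 1).
4. State that the 43% figure describes the VRM-inclusive composite. A two-component version would rest on one low-risk warfarin event in 343.5 pt-yr (0.29%), too few to be useful.

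The cost is wording and one recalculation, with no extra patients. The price is a less favourable description of the margin, and an effect-preservation figure that no longer directly supports the tested outcome.

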**Table 2. Event rates and confidence intervals for warfarin, DAPT, and apixaban in all-comer AVR population.**

Treatment in all-comer AVR population	Event rate (%/pt-yr)	Lower 95% CI (%/pt-yr)	Upper 95% CI (%/pt-yr)
Warfarin*	1.75%	1.09%	2.81%
DAPT†	10.65%	6.85%	16.28%
Apixaban†	1.00%	0.52%	1.66%
	1.25%	0.71%	1.98%
	1.50%	0.90%	2.30%
	1.75%	1.10%	2.60%
	2.00%	1.30%	2.91%
	2.25%	1.50%	3.21%
	2.50%	1.71%	3.51%
	3.00%	2.13%	4.10%
	4.00%	2.98%	5.27%
	5.00%	3.86%	6.42%

\* The confidence interval was estimated using the random effects HKSJ meta-analysis model; † The confidence intervals were estimated using Poisson distribution.

Assuming that the event rates for warfarin and apixaban would be similar, a conservative estimate of the treatment effect is 4.04%/pt-yr, which reflects the difference between the upper bound of the 95% CI of the pooled event rate of warfarin (2.81%/pt-yr) and the lower bound of the 95% CI of the event rate in DAPT (6.85%/pt-yr). The non-inferiority margin of 1.75%/pt-yr is approximately 43% (1.75/4.04) of the treatment effect and below ½ of the treatment effect as cited in the 2016 FDA guidance “Non-Inferiority Clinical Trials to Establish Effectiveness Guidance for Industry” ([CDER/FDA, 2016](#)).

With an accrual time of 1 year, an assumption that 50% of the expected number of participants will be enrolled in about 5 months (40% of the total accrual time), and a minimum follow-up period of 2 years, the assumed loss to follow-up rate for the period of 2 years is 5%, which is equivalent to a loss hazard rate of 0.026 for both the test and control groups. *Assuming a one-sided alpha of 2.5%, an approximate power of 90%, an equal event rate of 1.75%/pt-yr in both warfarin and apixaban arms, and an absolute NI margin of 1.75%/pt-yr, the estimated sample size is 990, therefore this study will recruit approximately 1000 participants.*

The major bleeding hazard rate for the control group is assumed to equal 3.63%/pt-yr ([Puskas et al., 2018](#)). The reference value was calculated by summing up numbers of events and follow-up years from both high and low risk controls. Using the proposed sample size of 1000, a superiority test for major bleeding has 90% power to detect a difference of 2.13%/pt-yr (i.e., 3.63%/pt-yr for warfarin arm and 1.5%/pt-yr for apixaban arm).

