## 11 References for sample size calculation

**Table 3. References used to estimate the primary outcome rate of warfarin (%/pt-yr).**

Author	Chambers	McNicholas	On-X Original PMA# P000037	PROACT		Tossios	Wu
				High Risk Control	Low Risk Control		
Year	2013	2006	2001	2018		2007	2006
Country	UK, Spain, Greece	USA	Germany, Spain, Greece	US, Canada		Germany	South Africa
Sample size	214	142	184	190	102	264	104
% of total	18%	12%	15%	16%	9%	22%	9%
Mean patient age (yrs)	59.7	58.6	60.2	55.8	52.5	62	39.7
Median Follow-up (yrs)	5.5	4.5*	2.2*	5.7	3.4	3.9	1.8*
Total Follow-up (pt-yr)	1360	659	411.8	1090	343.5	1069.4	172.5
Target INR	2.0-3.0	2.5-3.5	SoC	2.0-3.0	2.0-3.0	2.5-3.5	1.5-2.5
Mean INR	NR	NR	NR	2.5	NR	NR	43% out of range
NR = Not Reported in the manuscript; * Mean follow-up (yrs) was reported;							
Number of events							
- TE †	8	6	7	19	1	16	2
- Thrombosis	0	0	0	2	0	0	0
- VRM	7	5	1	7	4	19	7
- % TEs in VRM	NR	NR	NR	NR	NR	26% §	NR
Total number of events with 26% reduction to VRM for TE overlap (r)§	13.2	9.7	7.7	30.1 #		30.1	7.2
Linearized event rate with 26% Reduction to VRM for TE overlap (<math>\lambda</math>)§	0.97%	1.47%	1.88%	2.10% #		2.81%	4.16%
Standard error of linearized event rate‡	0.0027	0.0047	0.0068	0.0038		0.0051	0.0155

† Peripheral TE was included if provided; § A 26% VRM was assumed to be related to TE event; # calculated by summing up numbers of events and follow-up years from both high and low risk controls; ‡ calculated as  $\lambda/\sqrt{r}$

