**Table 4. Estimated event rates of standard warfarin and DAPT for low risk patients in the PROACT trial.**

	Standard Warfarin (INR 2.0-3.0)	DAPT
Total Follow-up (pt-yr)	343.5 pt-yr	288.1 pt-yr
Sample size	102	99
Number of all TE	1	14
Number of thrombosis	0	4
Number of VRM	4	3
Total number of events with 26% reduction to VRM for TE overlap	4.0	20.2
Linearized event rate with 26% Reduction to VRM for TE overlap	1.15%	7.02%

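### Section 8.2 names PROACT as the exception to double counting, yet the margin justification applies the 26% cut to PROACT; without it the margin is about 55 to 67% of the warfarin effect, not 43%.

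*Combined protocol and SAP*

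**What the plan says.** Protocol 8.2 estimates warfarin and DAPT event rates from TE, thrombosis and VRM. On how the sources count deaths it says: "Except for the PROACT clinical trial data, the publications report the non-hierarchical event rate for VRM and TE". The consequence follows at once: "If a participant died due to a TE, it would be counted in both the VRM and the TE rate". This is the only reason given for the reduction. The fraction comes from a single-centre study in which 5 of 19 valve-related deaths were due to TE. Section 8.2 then assumes 26% for any publication that did not report its TE deaths.

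The Table 3 footnote reads "A 26% VRM was assumed to be related to TE event". Table 3 gives the pooled PROACT controls 30.1 events after the cut and marks the TE share of VRM in PROACT as not reported. The row "Total number of events with 26% reduction to VRM for TE overlap" in Table 4 gives 4.0 events for low-risk warfarin and 20.2 for DAPT, both PROACT arms.

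Those counts feed the margin argument: "therefore the conversion factor was calculated to be 1.52 (= 1.75/1.15"). The factor scales the low-risk DAPT rate to all-comers, with a lower limit of 6.85%/pt-yr. Subtracting the upper warfarin limit of 2.81 leaves an effect of 4.04. The margin "is approximately 43% (1.75/4.04) of the treatment effect", and the protocol adds that this is below one half.

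**The concern.** If PROACT is the exception to double counting, the stated reason for the cut does not apply to it. The cut then removes real events from the low-risk warfarin arm, which is the denominator of the conversion factor. A lower denominator raises the factor, the all-comer DAPT rate and the apparent warfarin effect, and makes the margin look like a smaller share of that effect.

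At stake is the statement that the margin preserves more than half of the warfarin effect. Protocol 8.2 offers the calculation as confirmation of the margin. SAP version 1.4 still refers to 8.2 for the justification (6.1.8) and still tests against 1.75%/pt-yr (6.3.1), so the point survives the early stop recorded in SAP 6.1.3.

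**Working it through.** **Inputs**
- Margin: 1.75%/pt-yr (8.2).
- Pooled warfarin rate: 1.75, upper limit 2.81 (8.2, Table 2).
- Low-risk warfarin: 1 TE, 0 thrombosis, 4 VRM, 343.5 pt-yr (Table 4).
- DAPT: 14 TE, 4 thrombosis, 3 VRM, 288.1 pt-yr (Table 4).
- PROACT controls, high and low risk together: 22 TE or thrombosis, 11 VRM, 1090 + 343.5 = 1433.5 pt-yr (Table 3).

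**Formula**

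Share = margin / [DAPT lower limit × (pooled warfarin rate / low-risk warfarin rate) − pooled upper limit].

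**1. The plan's figure reproduces**
- Cut counts: 22 + 0.74 × 11 = 30.14; 1 + 0.74 × 4 = 3.96; 18 + 0.74 × 3 = 20.22.
- Low-risk warfarin: 3.96/343.5 = 1.153%; factor 1.75/1.153 = 1.518.
- DAPT lower limit: 13.00/288.1 = 4.512%; all-comers 4.512 × 1.518 = 6.85.
- Effect: 6.85 − 2.81 = 4.04; share 1.75/4.04 = 43%.

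**2. No cut in the PROACT low-risk arms, stated pooled rate kept**
- Low-risk warfarin: 5/343.5 = 1.456%; factor 1.75/1.456 = 1.202.
- DAPT: 21 events; exact Poisson lower limit 13.00, again 4.512%.
- All-comers: 4.512 × 1.202 = 5.42; effect 5.42 − 2.81 = 2.61; share 1.75/2.61 = 67%.

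The DAPT lower limit does not move, so the whole change comes from the factor.

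**3. Pooled rate corrected as well**

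PROACT in Table 3 becomes 33/1433.5 = 2.30% instead of 30.14/1433.5 = 2.10%. The stated pooled 1.75 (1.09, 2.81) does not reproduce from Table 3. With the printed counts, the six studies give about 2.00 (1.20, 3.34) on the log scale with the HKSJ interval, and 1.88 to 1.93 on the raw scale. The corrected share is therefore a range:

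| Pooled rate with 33 PROACT events | DAPT lower limit, all-comers | Effect | Share |
|---|---|---|---|
| Stated values scaled by the shift in the re-run: 1.784, upper 2.876 | 4.512 × 1.784/1.456 = 5.53 | 2.65 | 66% |
| Log-scale re-run: 2.04, upper 3.41 | 4.512 × 2.04/1.456 = 6.32 | 2.91 | 60% |
| Raw-scale re-run (DerSimonian-Laird): 1.954, upper 2.893 | 4.512 × 1.954/1.456 = 6.06 | 3.16 | 55% |

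**4. The printed DAPT limits mix counts**

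13.00 is the exact lower limit for 21 events; 30.89 is the upper limit for 20. For 20.22 events the lower limit is 12.39. With the cut kept throughout: 12.39/288.1 = 4.30%; 4.30 × 1.518 = 6.53; 6.53 − 2.81 = 3.72; 1.75/3.72 = 47%.

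**5. Where the result turns**

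The share is one half when the effect is 3.50, so when the all-comer DAPT lower limit is 6.31. With the stated pooled rate and a DAPT limit of 4.512, the low-risk warfarin rate must then be 4.512 × 1.75/6.31 = 1.251%, or 1.251% × 343.5 = 4.3 events. The arm had one TE, so its true overlap is 0 or 1 death; the cut removes 0.26 × 4 = 1.04. If that TE was fatal and the DAPT arm had no overlap, the counts are 4 and 21: 4/343.5 = 1.164%; 4.512 × 1.75/1.164 = 6.78; 6.78 − 2.81 = 3.97; share 44%.

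**6. The remark on a 5% apixaban rate**

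Table 2 gives that rate an upper limit of 6.42. Without the cut, the DAPT lower limit is 5.42 with the stated pooled rate kept and 5.53 to 6.32 in the table above. All are below 6.42, so the claimed separation is lost.

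**The case against.** The best defence is the wording of the next rule. Section 8.2 assumes 26% for any publication that did not report its TE deaths, and Table 3 marks PROACT as not reported. Read literally, the rule covers PROACT, and the cut is labelled openly in 8.2 and both tables. This stands in part. Section 8.2 never says that PROACT needs no cut; that is an inference from the named exception. A reader might conclude that the plan's own method gives 67%. The documents do not support that: one reading gives 43% as printed, the other gives the higher share, and only PROACT's own counts can decide. What remains is that the sentence and the tables cannot both be right.

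It is also fair that the 67% keeps a pooled rate containing cut PROACT data, and that the 60% should not be set against 43%. The same log-scale re-run with the cut kept gives about 39% (4.512 × 2.00/1.153 = 7.83; 7.83 − 3.34 = 4.49; 1.75/4.49). Hence a range, not one figure.

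The shift rests on about one event, and 26% is an assumed average rather than a patient count. A removal of 1.04 deaths therefore strains plausibility but is not itself a contradiction. It does show how fragile the printed share is.

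Finally, the protocol "set the non-inferiority margin for this study at 1.75%/pt-yr, equivalent to a doubling of the estimated event rate in warfarin arm"; the effect calculation only confirms it. A reader might infer that the non-inferiority test is invalid. That does not follow: hypothesis, decision rule and the OPC co-primary do not use the 43%. The 5% remark is likewise illustrative, since such a rate already exceeds the 3.4%/pt-yr OPC limit.

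**Conclusion.** The inconsistency is certain; its size is conditional. If PROACT's VRM and TE counts do not overlap, the margin is about 67% of the warfarin effect with the stated pooled rate kept, and about 55 to 66% with the pooled rate corrected. The below-one-half statement fails in every one of these versions. The second range carries the further caveat that the stated pooled rate does not reproduce from Table 3. If the cut is right for PROACT, the exception sentence is wrong and the share is about 47% once the DAPT limit comes from one count, still below one half. The plan's other assumptions are taken as given, including DAPT as a placebo equivalent and the constant conversion factor.

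**What to change.** - Replace the 26% borrowed from another study with PROACT's actual number of TE deaths counted in both VRM and TE, by arm, and make the exception sentence in 8.2 agree with Tables 2 to 4.
- Recompute the low-risk warfarin and DAPT rates, the pooled rate with its interval, the conversion factor, the DAPT limits (both from the same count), the effect and the margin share.
- If there is no overlap, state that the share is above one half (roughly 55 to 67%, depending on the pooled rate). Delete the below-one-half statement and the remark about a 5% apixaban rate.
- If there is overlap, correct the exception sentence and report the share that the actual counts give.
- Keep the pre-specified 1.75%/pt-yr test. No additional threshold is needed.

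The work is a look-up in the PROACT data plus corrections to text and tables. The price is that the margin justification becomes less favourable.
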